Notes review. During the available follow-up time (which will vary from 1 month to 2 years) all patient's notes will be reviewed to document returns, time to return, reasons for returns, complications, side effects, economic data (see below) and any subsequent referrals.¹⁹

Sample size Phase II. 'Medicalising' effect of using RADT. (alpha=0.05, beta=0.2). This is the limiting sample size calculation although not the primary outcome. A good proxy for 'medicalising' behaviour is the change in beliefs about the need to see doctors in future episodes – assuming there are 15% differences between groups (22% were observed in our previous trial) ²⁷ then only 152 patients per group are needed (see table below). However a harder behavioural outcome is preferable: to assess the medicalising effect on reattendance behaviour; if we assume that using RADTs may change subsequent attendance by 11% (RADT 38%, clinical score 27%, delayed prescribing 27%) - as observed in the medicalising effect of prescribing strategies in a previous trial over a similar follow-up period²⁷ - then 254 patients per group are needed or 849 in total allowing for 10% loss to follow-up of notes.³⁹ An alpha of 0.01 and beta 0.1 would require an unfeasibly large sample (460 per group or >1500 patients in total) or another 2 centres for the trial.

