Primary outcome: symptom severity (alpha= 0.01:beta=0.1). **Diary score.** The time when an RADT is most likely to help patients is when the inflammation due to bacterial infection is at its greatest in the first few days after seeing the doctor. We assume the minimum effect size for the symptoms severity score is a 0.33 standardised effect size (i.e. 0.33 SD) on days 2-5 is when patients rate their sore throat at its worst. To detect a 0.33 standardised effect size difference between the RADT group and control groups (assuming both control groups are 0.33 SD higher than the RADT group) requires a minimum of 134 per group (for alpha=0.05,beta=0.2) but preferably for (for alpha=0.01 and beta=0.1), 242 per group, or 909 patients in total allowing for 20% loss to follow-up of diary information.^{27;30} A standardised effect size of 0.33 is classified as a small effect size, (0.33 SD is equivalent to half patients rating sore throat a mild rather than moderately bad problem, or duration of sore throat one days difference), and in this context this order of effect size was judged to be the smallest worthy of treatment by general practitioners.³⁰ A much smaller effect size (e.g. 0.25standardised effect size) would result in an unfeasibly large sample (see table below). We will explore in the phase 1 (including the qualitative work) whether such an effect size (i.e. 0.33 SD) is regarded by patients as being the minimal worth treating, and what effect size would be regarded as equivalent. An alpha of 0.01 is preferable since it allows for type I error - with 2 comparisons between RADT and the other two groups, and also for multiple outcomes (severity/duration), and a beta of 0.1 will help ensure that we do not miss an effect in our primary outcome.

outcome are in bold).	Difference between RADT group and other two groups	Alpha 0.01 Beta=0.1	Alpha 0.01 Beta=0.2	Alpha 0.05 beta=0.2
Standardised effect size (continuous outcomes e.g. symptom severity,duration, time to first return for sore throat)	0.5 (i.e. RADT 0.5 lower than other 2 groups)	107	85	59
	0.33	242	193	134
	0.25	420	335	233
'Medicalisation' and antibiotic use:				
Proportions: behaviour (return to surgery); antibiotic use	11% (38%, 27%, 27%)	460	366	254
	15% (42%, 27%, 27%)	253	202	140
	20% (47%, 27%, 27%)	146	117	81
Proportions: beliefs (in the need to see the doctor; belief in antibiotics)	15% (57%,57%,72%)	274	219	152
	20% (57%, 57%, 77%)	152	121	84

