Sample size in each group¹-range of options for Phase II trial (our proposed sample sizes for each outcome are in **bold**).

1. We used the NQUERY multiple group sample size programme for three groups and assumed both clinical score and control groups had similar figures; if the control group fares worse than the clinical score group (i.e. the spread of observations is wider) fewer numbers will be needed in each group. The numbers in each cell are the numbers with complete data required in each group.

Statistics analysis, type and frequency

We will perform analysis of covariance for the main continuous outcomes (diary scores, symptom duration). Log rank tests and Cox regression will be used to assess the time to return to the surgery with a new episode of sore throat as we used in our previous trial¹⁹ (which will involve 'censored' data due to variable follow-up time available). Logistic regression will be used for dichotomised outcomes (e.g. belief in the need to see the doctor, belief in antibiotics) and Poisson regression for incidence rates (e.g. rates of return to the surgery with sore throat - which more closely follow a Poisson distribution rather than a normal distribution). The models will control for confounders if appropriate (although randomisation should ensure that confounders are balanced between groups). We will present the results with 95% confidence intervals. The primary analysis will be an intention to treat analysis based on finding the differences proposed. We will specify *a priori* key subgroups as potential effect modifiers based on an updated literature review prior to analysis (currently we specify baseline symptom severity, and GPs' view of whether the infection is viral or bacterial). We will also perform secondary analyses: a) a per protocol analysis, and also b) an equivalence analysis if appropriate (having established in our qualitative work what patients regard as equivalent). The clinical and demographic characteristics of a) eligible patients not consenting, and also b) those not followed up, will be compared to assess respectively possible selection and non response bias.

Our key presentation of the data will be of the main symptomatic outcomes alongside the data on antibiotic use and side effects from antibiotics

Economic analysis.

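### The Phase II sample size table sizes time to first return for sore throat as a fully observed continuous outcome, although the protocol expects most patients to be censored

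*Protocol*

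**What the plan says.** The protocol treats return to the surgery in three places.

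- **Sample size table, Phase II.** The standardised-effect row for continuous outcomes gives as examples "symptom severity,duration, time to first return for sore throat". For 0.33 SD it prints 242, 193 and 134 per group, for alpha 0.01/beta 0.1, alpha 0.01/beta 0.2 and alpha 0.05/beta 0.2. The footnote states the method, "We used the NQUERY multiple group sample size programme for three groups and assumed both clinical score and control groups had similar figures", and what a cell means: "The numbers in each cell are the numbers with complete data required in each group".
- **Statistics analysis, type and frequency.** Time to return with a new sore throat is analysed by log rank tests and Cox regression, "which will involve 'censored' data due to variable follow-up time available".
- **Sample size Phase II, text on medicalising effects.** Return behaviour is sized as a proportion, "RADT 38%, clinical score 27%, delayed prescribing 27" per cent. This needs 254 per group at alpha 0.05/beta 0.2, or 849 in total with 10% loss of notes. At alpha 0.01/beta 0.1 the same text gives 460 per group and calls the resulting total unfeasible.

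The prose attaches the 242 to the diary score. Its heading is "Primary outcome: symptom severity (alpha= 0.01:beta=0.1", and the size is "preferably for (for alpha=0.01 and beta=0.1), 242 per group, or 909 patients in total allowing for 20% loss to follow-up of diary information".

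**The concern.** A standardised mean difference can size an outcome only if each patient contributes a measured value. On the protocol's own rates, 62% to 73% of patients will have no observed return. The power of a log rank or Cox analysis depends on the number of returns, not on the number of patients followed.

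The table is also hard to reconcile with itself. At the same error rates it asks for 242 per group for time to return and 460 for the proportion returning, which is nearly a twofold difference for two measures of the same behaviour.

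Return behaviour is the outcome the protocol prefers, as the harder one, for judging whether rapid tests medicalise sore throat. Someone who took the continuous row at face value could read a null log rank result as stronger evidence against medicalisation than it would be.

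**Working it through.** **Inputs from the protocol.** Effect 0.33 SD, with the RADT group differing from two equal groups; 242 and 134 per group; return proportions 38%, 27%, 27%; 909 patients in total; 10% loss of notes.

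**1. Reproduce the row.** Three-group one-way ANOVA with non-centrality λ = n × d² × 2/3.
- n = 242: λ = 242 × 0.1089 × 2/3 = 17.57; power at alpha 0.01 is 90.1%.
- n = 134: λ = 134 × 0.1089 × 2/3 = 9.73; power at alpha 0.05 is 80.1%.

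The printed sizes are exact for fully observed data and contain no allowance for censoring.

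**2. Reproduce the proportions row.** Chi-square test on 2 df, with λ = n × Σ(pᵢ − p̄)² / [p̄(1 − p̄)] and p̄ = 0.92/3 = 0.3067, so λ = 0.03794 × n.
- n = 460: λ = 17.45; power at alpha 0.01 is 90%.
- n = 254: λ = 9.64; power at alpha 0.05 is 80%.

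The same method applied to the sizes in the continuous row gives 56% at 242 per group and alpha 0.01, and 51% at 134 per group and alpha 0.05. This cross-check needs no survival assumption.

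**3. Log rank power.** Assume proportional hazards and a common follow-up period to which the 38% and 27% apply.
- Hazard ratio = ln(0.62)/ln(0.73) = 1.519, and ln(1.519) = 0.418.
- Total returns D = n × (0.38 + 0.27 + 0.27) = 0.92n.
- Three-group test: λ = D × (ln HR)² × (1/3)(2/3) = 0.03883 × D, on 2 df.

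| Per group | Returns | λ | Alpha | Power |
|---|---|---|---|---|
| 242 | 223 | 8.65 | 0.01 | 53% |
| 134 | 123 | 4.79 | 0.05 | 49% |
| 273 | 251 | 9.75 | 0.01 | 60% |
| 273 | 251 | 9.75 | 0.05 | 80% |

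The 273 is 909 × 0.9 / 3. With complete data, 242 per group would supply 726 observed times; here there are about 223.

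**4. Simulation.** At 242 per group and alpha 0.01, simulated exponential times with a common follow-up gave 58% (HR 1.52, 1,500 runs) and 59% (HR 1.53, 4,000 runs), a little above the formula.

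**5. Sensitivity at 242 per group, alpha 0.01.**
- Control return rate 20% to 35% with HR 1.52: 38% to 68%.
- 0.33 SD read on the log-time scale of an exponential: HR = exp(0.33 × 1.283) = 1.53, power 55%.
- 0.33 SD read on the raw mean scale: HR = 1/0.67 = 1.49, power 48%.
- RADT against the other two groups pooled, HR 1.52: 64% by formula.

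**6. Returns needed at HR 1.52.**
- Alpha 0.01/beta 0.1: λ = 17.43, so D = 17.43/0.03883, about 449 returns, or 449/0.92, about 488 per group.
- Alpha 0.05/beta 0.2: λ = 9.635, so D is about 248 returns, or about 270 per group.

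**The case against.** A reader might infer from the table that the protocol promises 90% power at the 1% level for time to return, and that the trial falls far short of it. The documents do not support that reading.

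- The prose makes the 1%/90% claim only for symptom severity: "To detect a 0.33 standardised effect size difference between the RADT group and control groups (assuming both control groups are 0.33 SD higher" concerns the diary score. Time to return is only an example in a row label.
- The table offers a range of options and marks the proposed sizes in bold. The bold does not survive in the available text, so which cell, if any, was proposed for this outcome cannot be seen.
- The text on medicalising effects already says that 1%/90% is out of reach for return behaviour, and sizes it at 5%/80%.
- The 242 counts patients with diary data. Returns come from notes review with 10% loss, so about 273 per group should contribute. At 5% that gives about 80% power, the protocol's own target for medicalising outcomes.
- The protocol does not say on what scale 0.33 SD of a return time is measured, so any single power figure rests on a conversion.
- Results are to be presented with 95% confidence intervals, which would show the imprecision of a null finding.

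All of this stands, and it limits the point to the table. It does not rescue the row. The label says these sizes serve time to return, the footnote says they require complete data, and the analysis section says the data will be censored.

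**Conclusion.** The row is wrong as written for time to first return, in every column. At the protocol's own return rates, three-group log rank power is roughly 53% by formula (58% to 59% by simulation) where the row implies 90%, and about 49% where it implies 80%. These figures assume proportional hazards, a hazard ratio of about 1.52 and 27% returning in the two comparison groups. They move with the return rate and time scale, but every variant computed at 242 per group and alpha 0.01 stays well below 90%.

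The error concerns a secondary outcome. The sizing of the primary symptom score reproduces exactly, and planned recruitment already gives about 80% power for time to return at the 5% level. The correction is to the stated figures, not to the design.

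**What to change.** Remove the time-to-first-return item from the continuous row and add a row sized by returns, with its assumptions stated: proportional hazards, 38% against 27% and 27% returning, hazard ratio 1.52, three-group log rank test. The entries would be about 449 returns (about 488 per group) for alpha 0.01/beta 0.1 and about 248 returns (about 270 per group) for alpha 0.05/beta 0.2.

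Add one sentence saying that 909 patients less 10% loss of notes, about 273 per group, give about 80% power at the 5% level and about 60% at the 1% level for this outcome.

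The cost is one table row and one sentence. Recruitment and analysis do not change; the only downside is a less favourable stated figure for this outcome.

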Clinical measures. Baseline proforma. In order to develop a clinical rule to predict bacterial infection, clinical features need to be compared with the results of the throat swab. GPs/Nurses will fill in the clinical details at baseline. This will consist of a single clinical sheet documenting baseline clinical data. We will collect data at presentation on temperature (using tempadot thermometers), the presence and severity of baseline symptoms (sore throat, difficulty swallowing, fever during the illness, runny nose, cough, feeling unwell, diarrhoea, vomiting, headache, muscles ache, abdominal pain, sleep disturbance, interference with normal activities) on 4

point Likert scales (none, a slight problem, a moderately bad problem, a bad problem), and the presence of signs (pus, nodes, tender nodes, temperature) based on previous clinical scores^{25 6 26 18}. The severity of symptoms not simply their presence is probably important: in piloting among 60 patients we have shown that the severity of symptoms rather than the presence of symptoms predicts bacterial infection which we documented by a four fold rise in antibody titres.

• Other clinical outcomes.

Symptom diary. Patients will fill a validated symptom dairy (as in phase 2). As in previous studies patients will be contacted when the research centre has received the consent form to check there are no problems filling in diaries.

If no diary is received after 2 - 3 weeks, one mailed reminder will be sent using a brief questionnaire containing the key diary items; if no diary or questionnaire has been returned a brief phone call will clarify the duration and severity of symptoms and whether antibiotic were used; this method has been shown to be both acceptable to patients and allows significantly less bias from low response rates²⁷.

Notes review. Patients will be asked to fill in a FREEPOST card to return documenting reconsultation (for worsening of symptoms, presentation with new symptoms and/or complications); this data will also be assessed by a review of the GP's notes. Although notes will be the main way of determining adverse outcomes these cards will provide additional information since sometimes patients get worse (after they have stopped filling in their diaries) and or adverse events do not get recorded in notes. We will relate whether adverse outcomes occur to the presence or absence of Streptococcus, clinical presentation and management

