Diary scores.^{19:27} Each symptom is scored 0=no problem to 6=as bad as it could be: sore throat, difficulty swallowing, feeling unwell, fevers, sleep disturbance) which patients fill out on all days until their symptoms have resolved. A phone call from the research assistant (RA) in the first few days resolves any problems the patient may have filling out the diary. We have chose the two item score (sore throat, difficulty swallowing) as the main outcome as it is more reliable than either item alone and is internally reliable (Cronbach's alpha=0.92); these simple diaries have been used in several of our studies^{27;30;39} and are also more sensitive to change than criterion measures.⁴⁰ Temperature will be taken by patients and documented on a daily basis in the diary using tempadot thermometers as in our previous studies.^{19 39}

Duration of illness. The diaries will also allow us to document duration of illness (until very little/no problem), the duration of moderately bad illness (until rated less than a moderately bad problem)³⁰, antibiotic use, and use of over the counter medicines (also see notes review)

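### Symptom duration is a time-to-resolution outcome but is assigned to ANCOVA, which has no proper place for returned diaries that stop before resolution

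*Protocol*

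**What the plan says.** Under *Statistics analysis, type and frequency*, the Protocol states: "We will perform analysis of covariance for the main continuous outcomes (diary scores, symptom duration". The next sentence assigns log-rank tests and Cox regression to time to return to the surgery with a new episode, "which will involve 'censored' data due to variable follow-up time available".

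Under *Duration of illness* (Phase 2 outcomes), the diaries are to give two durations: "duration of illness (until very little/no problem), the duration of moderately bad illness (until rated less than a moderately bad problem". Under *Diary scores*, the diary is one "which patients fill out on all days until their symptoms have resolved". No fixed last diary day is given.

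Under *Sample size Phase II*, severity is named as primary: "Primary outcome: symptom severity (alpha= 0.01:beta=0.1". The alpha of 0.01 is justified partly by there being two symptom outcomes, severity and duration. The total includes an allowance for "20% loss to follow-up of diary information".

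Two remarks in the Phase 1 text bear on incomplete diaries. The notes review paragraph says that "sometimes patients get worse (after they have stopped filling in their diaries". The symptom diary paragraph describes a mailed questionnaire when no diary arrives and then a further step: "if no diary or questionnaire has been returned a brief phone call will clarify the duration and severity of symptoms".

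**The concern.** Each duration is the time to an event: the first day on which symptoms fall to the stated level. If a patient returns a diary that ends before that day, the duration is right-censored. An analysis of covariance needs one completed number per patient, so such a patient is dropped, is given the last diary day as the duration, or has a value imputed. The first two can shrink a real difference, because longer illnesses have more days on which the diary can be abandoned.

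Duration is not primary, but it matters. It is one of the two symptom outcomes behind the choice of alpha, and it enters the cost-consequence analysis and the planned cost per day with sore throat. The Protocol also allows a secondary equivalence analysis. If that were applied to duration, a difference shrunk towards zero would favour a finding of equivalence.

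**Working it through.** **1. The plan's own figures.** For three equal groups with means 0, 0.33 and 0.33 SD, alpha 0.01 and power 90%, the one-way ANOVA (noncentral F) calculation gives 242 per group, as stated. With 20% loss, 242/0.8 = 302.5, rounded up to 303, and 3 × 303 = 909, as stated. The Protocol equates 0.33 SD with one day of sore throat, so the implied SD is 1/0.33 = 3.03 days.

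**2. Inputs.** From the Protocol: SD about 3 days, difference 1 day, 242 per arm, alpha 0.01. Assumed, because the Protocol gives no figure: gamma or log-normal durations in whole days, control mean 5 or 6 days, and a constant daily chance *h* of stopping the diary, the same in every arm.

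**3. Who is lost.** An illness of *x* days is seen to end with probability (1−h)^(x−1).
- h = 2%: a 5-day illness is unresolved in 1 − 0.98^4 = 7.8% of diaries, a 10-day illness in 1 − 0.98^9 = 16.6%.
- h = 4%: 1 − 0.96^4 = 15.1% and 1 − 0.96^9 = 30.7%.

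**4. Dropping unresolved diaries.** To first order, the mean among resolved diaries falls by h × SD². The difference therefore falls by h × (SD²control − SD²RADT).
- Same SD in both arms: no shrinkage.
- SD proportional to the mean (means 5 and 4, SDs 3 and 2.4): 0.04 × (9.00 − 5.76) = 0.13 day at h = 4%, and 0.02 × 3.24 = 0.065 day at h = 2%.

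**5. Taking the last entry as resolution.** The expected recorded duration is [1 − (1−h)^x]/h, so one further day of illness adds (1−h)^x instead of 1. At x = 5 this is 0.98^5 = 0.904 (shrinkage 9.6%) or 0.96^5 = 0.815 (18.5%).

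**6. Simulation.** With 242 per arm, alpha 0.01 and 600 trials per setting:

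| Unresolved | Shrinkage, dropped | Shrinkage, last day | t-test power, dropped | t-test power, last day | Log-rank power |
|---|---|---|---|---|---|
| none | 0 | 0 | 91-93% | 91-93% | 90-92% |
| 8-9% | 5-6% | 11-13% | 86-91% | 81-89% | 88-92% |
| 14-18% | 9-12% | 21-24% | 81-86% | 71-79% | 86-90% |

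A separate run with 8-19% unresolved gave 0-5% (dropped) and 7-21% (last day), with log-rank power often no better than that of the t-test. Step 4 shows why the effect of dropping ranges down to zero: it depends on whether the spread differs between arms. Taken together, a one-day difference would be estimated as 0.88-1.00 day if unresolved diaries are dropped, and 0.76-0.93 day if the last entry is used.

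**7. Skewness alone.** With complete, skewed gamma durations (skewness about 1.2) and 242 per arm, the t-test type I error was 0.010 at alpha 0.01 and 0.052 at 0.05.

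**8. A fixed diary end instead of random stopping.** Gamma durations, control means of 4-7 days, capped values kept as complete: a 14-day cap recovers 96-97% of the difference, a 10-day cap 75-88%, a 7-day cap 39-69%. The Protocol states no cap.

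**The case against.** The case on the other side is substantial, and much of it stands.

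- **The documents do not describe censored diaries.** Patients are told to continue until resolution, and there is no 14- or 21-day cut-off. This stands as to amount: the share that stops early is an assumption. But the instruction does not guarantee compliance. The Phase 1 text accepts that patients stop and then worsen, although it does not say whether they had first recovered.
- **The 20% allowance** might be read as a censoring rate. It is not. The sample size table counts patients with complete data, so the 20% is missing information, which Cox regression would not recover.
- **Duration is recovered by questionnaire and telephone.** This is written for Phase 1 and is likely but not explicit for Phase 2. It applies when nothing has been returned, not to a returned diary that ends early.
- **An analysis plan may set the handling rule**, including imputation. That is fair, and the absence of a rule is not the point here. The point is the method that the Protocol names.
- **The contrast with time to return is reasoned.** The Protocol justifies Cox regression there by variable follow-up of 1 month to 2 years. So this is not a contradiction, only a method already in the plan that suits duration too.
- **Power.** A reader might infer that log-rank is the more powerful test. That is not established. On log-normal durations with SD 3 days and a 14- or 21-day cap, the linear model had 87-96% power against 80-87% for log-rank.
- **Cost per day** needs mean days, which a hazard ratio does not supply. This stands, and the fix allows for it.

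**Conclusion.** The point holds in a limited form. The Protocol defines duration as time to resolution and assigns it a method that cannot properly use returned diaries ending before resolution. If about 8-19% of diaries do so, equally in all arms, a one-day difference shrinks by roughly 0-12% when those patients are dropped, and by 7-24% when the last entry is taken as resolution. This rests on the implied SD of about 3 days and on assumed distributions, control means and stopping rates.

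Two stronger readings are tempting and are not supported. One is that skewness biases the comparison: at this sample size it does not. The other is that ANCOVA is bound to pull the estimate towards no difference: with complete diaries there is no bias, and if stopping differs between arms the error could go either way. The primary severity outcome and the total of 909 do not depend on this point. The change is still worth making, because it removes a foreseeable attenuation at little cost.

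**What to change.** Amend the analysis section as follows:

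- Keep ANCOVA for the severity score.
- Analyse both duration outcomes by log-rank test and Cox regression, as for time to return. The event is the first day at the stated threshold. Unresolved diaries are censored at the last completed day. Use the same baseline covariates.
- Report medians by arm beside the hazard ratio, with intervals.
- Keep an estimate of mean or restricted mean days for the cost per day with sore throat.

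The cost is a sentence or two and no extra data. A hazard ratio is harder to explain than a difference in days, and the test may have slightly less power when diaries are complete. The method also assumes that stopping the diary is unrelated to the remaining length of illness. Where that fails, Cox regression is biased too, so the number of unresolved diaries should be reported by arm.

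### Poisson regression is fixed for rates of return to the surgery with no allowance for overdispersion, so intervals for this secondary analysis are too narrow if patients' return rates differ beyond the covariates

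*Protocol*

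**What the plan says.** The protocol section Statistics analysis, type and frequency assigns one model family to each type of outcome. For return counts it names "Poisson regression for incidence rates (e.g. rates of return to the surgery with sore throat" and gives as its reason that they are rates "which more closely follow a Poisson distribution rather than a normal distribution". It mentions no dispersion parameter, robust variance or negative binomial model. On adjustment it says "The models will control for confounders if appropriate", and on reporting, "We will present the results with 95% confidence intervals".

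The same section analyses return behaviour in a second way: "Log rank tests and Cox regression will be used to assess the time to return to the surgery with a new episode of sore throat". Beliefs about needing the doctor go to logistic regression.

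The follow-up behind the counts is set under Notes review: "During the available follow-up time (which will vary from 1 month to 2 years". Under Sample size Phase II, reattendance is powered as a proportion returning (38%, 27%, 27%), with the parameters "alpha=0.05, beta=0.2). This is the limiting sample size calculation although not the primary outcome".

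**The concern.** The stated reason compares Poisson with normal, which concerns the skewed, discrete shape of counts. The width of a Poisson interval depends on something else: that the variance of the count equals its mean once arm, covariates and person-time are in the model. Repeat visits by the same person are a familiar case where this fails. The protocol itself treats reattendance as depending on a patient's beliefs about seeing the doctor, and these differ between people. Adjustment, which is itself conditional, can remove only the measured part of such differences. The long and unequal follow-up adds to the problem, because the excess variance grows with the expected count.

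At stake is the rate ratio that compares repeat attendance between rapid testing and the other two strategies. A falsely precise ratio could suggest that a strategy raises or lowers reattendance when it does not. The economic section also names later consultation behaviour as a likely main driver of cost.

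**Working it through.** **1. The protocol's own figure.** Inputs from Sample size Phase II: 38%, 27%, 27%; alpha 0.05; power 80%; 10% loss.

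The three-group chi-square test (2 df) has noncentrality λ = n × Σ(pᵢ − p̄)² / [p̄(1 − p̄)].
- p̄ = 0.92/3 = 0.3067; Σ(pᵢ − p̄)² = 0.008067; p̄(1 − p̄) = 0.21262.
- λ = n × 0.03794. At n = 254, λ = 9.636 and power is 80.0%; at n = 253 power is 79.8%.
- With losses: 254/0.9 = 282.2, rounded up to 283; 283 × 3 = 849.

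The stated 254 per group and 849 in total are reproduced. They rest on proportions, so the variance of a count does not enter.

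**2. Model for extra variation.** Let patient i have rate λ₀uᵢ per year over tᵢ years, where uᵢ is gamma distributed with mean 1 and variance k. k = 0 is pure Poisson. The protocol gives no count variance, so k = 0.5, 1 and 2 are assumptions.

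Per patient, variance/mean = 1 + kλ₀tᵢ. For an arm's total count over its person-time, the ratio is

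φ = 1 + kλ₀ × E[t²]/E[t].

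The true standard error is √φ times the Poisson one, and the actual size of a nominal 5% test is 2 × [1 − Φ(1.96/√φ)].

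**3. Follow-up.** The protocol gives the range only; a uniform spread from 1/12 to 2 years is assumed. E[t] = 1.0417, E[t²] = 1.3912, ratio = 1.3356.

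**4. Base rate.** λ₀ is set so that 27% return at least once, the protocol's figure for both comparison groups. This gives 0.350, 0.387 and 0.473 returns per year for k = 0.5, 1 and 2.

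**5. Closed-form result with no true difference.**
- k = 0.5: φ = 1 + 0.5 × 0.350 × 1.3356 = 1.234; √φ = 1.11; actual size 7.8%.
- k = 1: φ = 1 + 1 × 0.387 × 1.3356 = 1.517; √φ = 1.23; actual size 11.2%.
- k = 2: φ = 1 + 2 × 0.473 × 1.3356 = 2.263; √φ = 1.50; actual size 19.3%.

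**6. Simulation of the same setting.** 20,000 null trials per k, two arms of 254, person-time as denominator, no covariates:

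| k (assumed) | True SE / Poisson SE | Rejects, Poisson SE | Rejects, robust SE |
|---|---|---|---|
| 0 | 1.01 | 5.0% | 5.1% |
| 0.5 | 1.12 | 7.8% | 5.1% |
| 1 | 1.24 | 11.2% | 5.1% |
| 2 | 1.51 | 19.3% | 5.6% |

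**7. Under the planned difference (38% against 27%).** With equal follow-up and 254 per arm, the nominal 95% Poisson interval covers the true ratio 95.0%, 92.5%, 89.5% and 82.0% of the time for k = 0, 0.5, 1 and 2.

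**The case against.** The strongest reply is that the protocol names a model family for each outcome and a variance estimator for none. Poisson regression with a robust variance is still Poisson regression, so a statistical analysis plan could settle the matter without contradicting the protocol. This stands in part, and it is a reason to rate the point as minor. It does not dispose of the point, because the protocol goes beyond silence: it argues for its model, and the argument misses the assumption that matters.

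Three stronger readings are tempting, and the protocol supports none of them.
- A reader might infer that the plan assumes the same return rate for every patient. Poisson regression assumes a common rate only given arm, covariates and person-time. Adjustment is foreseen, and the term incidence rate already implies a person-time denominator, although no offset is spelled out.
- A reader might infer that the intervals are certain to be too narrow. The protocol gives no variance of return counts, and with k = 0 the test holds its 5%.
- A reader might infer that the whole assessment of medicalisation is compromised. Time to return (log rank, Cox) and beliefs (logistic) do not use the Poisson variance, and the powered reattendance measure is a proportion. The protocol also says that medicalisation is not the primary outcome.

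**Conclusion.** The point holds in a limited form. The protocol fixes Poisson regression for return rates on a ground that leaves overdispersion unaddressed. If return rates vary between patients beyond the modelled covariates, the model-based intervals for this one secondary rate-ratio analysis are too narrow. At 254 per arm and 27% returning, the false-positive rate is about 8%, 11% and 19% instead of 5% for frailty variances of 0.5, 1 and 2, and intervals of the right width would be about 12%, 24% and 51% wider.

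These sizes rest on assumed values of k, a gamma form, uniform follow-up and no covariate adjustment; adjustment that explained part of the variation would reduce them. The primary symptom outcome and the sample size of 254 per group are not touched. Severity is minor: a cheap improvement.

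**What to change.** In the section Statistics analysis, type and frequency, state that return rates will be analysed by negative binomial regression, or by Poisson regression with robust (sandwich) standard errors, in either case with log follow-up time as offset. Keep log rank and Cox for time to return, and logistic regression for beliefs. Of the two options only the robust variance was simulated here; it held 5.1% to 5.6% across k = 0 to 2.

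The cost is one phrase, with no new data and no change in sample size. Where overdispersion exists, intervals become wider and this analysis loses some apparent precision. Where it does not, almost nothing changes.
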